**ONZ-2023-0453**

**Statistical analysis plan**

**Version January 29, 2024**

1. Objective: The objective of this analysis plan is to assess the effectiveness of moderate continuous training combined with strength training versus high-intensity training combined with strength training in improving outcomes in patients with NAFLD over a 14-week intervention period.
2. Study Design:
  - a. Randomization: Patients will be randomly assigned to one of two arms:
    - Arm A: Moderate continuous training combined with strength training.
    - Arm B: High-intensity training combined with strength training.
  - b. Intervention: Patients will undergo the assigned exercise regimen for 14 weeks.
  - c. Outcome measures:

Primary outcome: liver function (fibroscan, echografie lever, biomarkers ALT/AST) and insulin sensitivity (glucose, insuline)

Secondary outcomes: length, weight, body composition (fat mass, fat free mass), exercise capacity (VO2max, strength), blood pressure, blood markers: lipid profile, IL-1beta, IL-6, IL-8 and TNF- $\alpha$ , quality of life
3. Data Collection:
  - a. Baseline assessment: We will collect demographic information (age, gender,...) and baseline measurements of outcome variables.
  - b. Intervention period: We will monitor adherence and possible adverse events to the exercise regimen
  - c. Follow-up: We will assess outcome measurements at the end of the 14-week intervention period.
4. Statistical Methods:
  - a. Data will be analyzed by SPSS.
  - b. Descriptive statistics: We will present baseline characteristics of participants in each study arm using means and standard deviations (continuous variables) or median (range), frequencies and percentages (categorical variables).
  - c. Primary analysis: We will conduct an intention-to-treat (ITT) analysis, including all randomized participants, regardless of adherence or dropout. We will compare the outcomes between the two study arms using mixed linear models
  - d. Sensitivity analysis: We will perform a per-protocol analysis, restricted to participants who completed the full 14-week intervention period and adhered to the exercise regimen. We will compare outcomes between study arms using similar statistical methods as in the primary analysis.
  - e. Subgroup analysis (if applicable): We will explore potential differences in treatment effects based on participant characteristics (e.g., age, gender, baseline disease severity) by conducting subgroup analyses. This can be

done by linear mixed models or regression analysis but will be determined once the dataset is finished.

- f. Missing data: We will assess the extent and pattern of missing data. If applicable, employ appropriate techniques (e.g., multiple imputation) to handle missing data and perform sensitivity analyses to evaluate the impact of missingness on the results.

5. A priori sample size: based on literature:

Group A: combined aerobic and strength training (primary outcome liver fat content): 30% (10,9%)

Group B: interval training (primary outcome liver fat content): 37% (12,4%)

Effect size is 0.5

Given alfa of 0.05, with a power to achieve of 0.8 we need 40 participants in each group. Accounting for a 15% drop out rate we will recruit 46 patients in each group

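### The primary outcome is a list of up to six measures with no decision rule, and the sample size rests on liver fat content, which the SAP does not link to any of them

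*SAP*

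**What the plan says.** Section 2c (Outcome measures) gives one entry for the primary outcome: "Primary outcome: liver function (fibroscan, echografie lever, biomarkers ALT/AST) and insulin sensitivity (glucose, insuline"). It covers two domains joined by a conjunction. Liver function holds Fibroscan, liver ultrasound, ALT and AST; insulin sensitivity holds glucose and insulin.

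Section 4c (Primary analysis) applies an intention-to-treat comparison to all of them alike: "We will compare the outcomes between the two study arms using mixed linear models". Neither section 4c nor any other part of section 4 says how several primary results combine into one conclusion.

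The only significance level is in section 5 (A priori sample size), which is introduced as based on literature. Its two group lines read "Group A: combined aerobic and strength training (primary outcome liver fat content): 30% (10,9"%) and "Group B: interval training (primary outcome liver fat content): 37% (12,4"%). It continues: "Effect size is 0.5" and "Given alfa of 0.05, with a power to achieve of 0.8 we need 40 participants in each group". Liver fat content is not among the primary or the secondary outcomes in section 2c.

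**The concern.** Two things that a SAP has to settle are open.

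The first is the decision rule. At least four readings fit the text:

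- success on any one measure is enough;
- every measure must succeed;
- each domain carries its own claim;
- liver fat content is the single lead measure.

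These have different error rates and different power. If ALT improved and insulin did not, the plan would define no conclusion, and the headline result could be picked after the data are seen.

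The second is the sample-size basis. The label in section 5 may describe the cited studies, or it may name this trial's lead measure. Fibroscan or ultrasound may have been meant to supply it, but section 2c files both under liver function and names no parameter. On either reading, the SAP does not tie its power statement to a measure it will analyse.

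**Working it through.** **Inputs from the SAP.** Number of primary measures k: six if ALT and AST are separate, five if ALT/AST is a ratio, four if glucose and insulin also form one index (section 2c). Number of domains: two. Alpha 0.05, power 0.8, effect size 0.5, 40 per group (section 5).

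**Assumptions, as the SAP gives none.** Each test is two-sided at 0.05. Test statistics are normal with a common correlation ρ between 0 and 0.9. The power figures take the planned 80% per test, with equal effects on all measures.

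**The plan's own figure.** For one two-sided comparison at effect size 0.5, n per group = 2(1.96 + 0.84)²/0.5² = 62.7, so 63 (64 with the t distribution), not 40. This discrepancy is a separate matter. It is not counted here, and nothing below depends on it.

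**Any one success counts.** With independence, the false-positive rate is 1 − 0.95^k:

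- k = 2: 1 − 0.9025 = 0.0975
- k = 4: 1 − 0.8145 = 0.186
- k = 5: 1 − 0.7738 = 0.226
- k = 6: 1 − 0.7351 = 0.265

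With correlation, write each statistic as √ρ·x + √(1−ρ)·eᵢ, where x and the eᵢ are independent standard normal. The rate is then 1 − ∫[Φ((1.96 − √ρ·x)/√(1−ρ)) − Φ((−1.96 − √ρ·x)/√(1−ρ))]^k φ(x)dx. Numerical integration gives:

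| k | ρ = 0 | ρ = 0.5 | ρ = 0.8 | ρ = 0.9 |
|---|---|---|---|---|
| 2 (one test per domain, or glucose and insulin) | 0.0975 | 0.091 | 0.078 | 0.070 |
| 4 (liver measures) | 0.186 | 0.156 | 0.114 | 0.094 |
| 5 | 0.226 | 0.183 | 0.127 | 0.102 |
| 6 | 0.265 | 0.207 | 0.139 | 0.108 |

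A separate simulation at ρ = 0.5 gave 0.090, 0.182 and 0.206 for k = 2, 5 and 6, which agrees.

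**A separate claim per domain.** The within-domain rates are the rows for k = 4 (9-19%) and k = 2 (7-10%).

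**All must succeed.** Alpha is protected. Eighty per cent power per test means a mean statistic of 1.96 + 0.84 = 2.80. With independence, joint power is 0.8^k: 0.640 for k = 2 and 0.262 for k = 6. With correlation it is ∫Φ((0.84 + √ρ·x)/√(1−ρ))^k φ(x)dx:

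| k | ρ = 0 | ρ = 0.5 | ρ = 0.8 | ρ = 0.9 |
|---|---|---|---|---|
| 2 | 0.640 | 0.687 | 0.729 | 0.750 |
| 6 | 0.262 | 0.478 | 0.616 | 0.675 |

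**Single lead measure.** One test at 0.05 gives 5%, with no inflation.

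**Cost of Holm.** Holm's first step tests at 0.05/k, with two-sided critical values of 2.24 (k = 2) and 2.64 (k = 6). The guaranteed power per measure is at least Φ(2.80 − 2.24) = 0.712 and Φ(2.80 − 2.64) = 0.565 (unrounded inputs). Restoring 80% at those levels multiplies the sample size by ((2.24 + 0.84)/2.80)² = 1.21 and ((2.64 + 0.84)/2.80)² = 1.54.

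**The case against.** The best defence has four parts.

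- **The sizing quantity is stated.** Section 5 names liver fat content twice and attaches the words primary outcome to it, so a reader could take it as the lead measure, with Fibroscan or ultrasound as the obvious source. This stands in part: the quantity is named, and what is missing is its link to section 2c. Even on this reading, the other listed measures remain primary with no rule.
- **The protocol may hold the definitions.** Which device and parameter gives liver fat, whether ALT/AST is a ratio, and whether glucose and insulin form an index may be set out there. That is fair, and a cross-reference would be enough for those details. It does not cover the decision rule and alpha handling, which belong in the SAP. This SAP states the primary outcome, the primary analysis and the sizing endpoint itself, and leaves them unconnected.
- **The magnitudes are illustrative.** This also stands. The SAP gives no correlation, sidedness or success rule. A common correlation across imaging, enzymes and glucose or insulin is a convenience. The upper ends require independence, which is unlikely for ALT with AST or glucose with insulin. The joint-power figures take the planned 80% as given and are not estimates of this trial's power.
- **A single primary measure is a preference.** It is one valid design. Several primaries under a stated rule are equally valid.

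**Conclusion.** The concern holds and must be fixed before analysis; confidence is high. The absence of a decision rule and of a link between sections 2c and 5 follows from the text alone and needs no numerical assumption. Only the size of the consequence is conditional: under any-one-counts the false-positive rate exceeds the nominal 5% throughout the range examined, and under all-must-succeed joint power stays below the planned 80% throughout. The one reading that avoids both problems, liver fat content as sole lead, has no named measurement in the SAP. Since the plan sets a significance level and a power target, it claims a confirmatory test and needs to say which test that is.

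**What to change.** Before any analysis, amend the SAP in one of two ways.

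1. **One primary measure.** Name it, test it once at two-sided 0.05, and state which existing measurement supplies it. If liver fat content is meant, say which device and parameter in section 2c gives it, or refer to where the protocol does. If not, choose a listed measure and restate the effect assumption, sample-size basis and power in section 5 for it. Move the other measures to secondary.
2. **Several primary measures**, for example one per domain, under a stated rule such as Holm, with power restated for that rule.

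Either way, say whether ALT/AST is one measure or two, and whether glucose and insulin are analysed separately or as an index.

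**Cost.** The change is to SAP wording, plus the protocol's outcome list if it repeats this one. No new measurement is needed if a listed one is chosen. Under the first option, the demoted measures lose stand-alone primary claims. A lead measure other than liver fat needs its own expected effect, which may make the stated power less favourable or change the recruitment target. Under the second, a planned 80% per test is guaranteed only as about 71% per measure for two primaries or 56% for six; guaranteeing 80% per measure would take about 21% or 54% more participants.

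### Does leaving the subgroup model open until the dataset is finished (SAP section 4e) call for a change to the plan?

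*SAP*

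**What the plan says.** Section 4e is headed "Subgroup analysis (if applicable" and states its purpose as follows: "We will explore potential differences in treatment effects based on participant characteristics (e.g., age, gender, baseline disease severity) by conducting subgroup analyses". On method, it says this can be "done by linear mixed models or regression analysis but will be determined once the dataset is finished". No other part of the SAP closes the list of factors, defines severity at baseline, names the outcomes to be examined by subgroup, or mentions an interaction term.

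The neighbouring items are more definite about the model. For the primary analysis, section 4c says "We will compare the outcomes between the two study arms using mixed linear models". For the per-protocol analysis, section 4d says "We will compare outcomes between study arms using similar statistical methods as in the primary analysis". Section 4f, on missing data, also leaves its technique open and offers multiple imputation only as an example.

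**The concern.** A SAP exists largely to fix analytic choices before results can influence them, and here it postpones one on purpose. The postponement does not seem necessary: section 4c has already chosen mixed linear models, section 4d carries that choice over to the per-protocol analysis, and the measurement times (baseline and the end of the 14 weeks) are known. The text does not say that the choice will be made without sight of results by arm. With an open list of factors and no stated interaction test, an analyst could try several models and factors and report the one that looks best.

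At stake is the credibility of any claim that one exercise regimen works better in a particular kind of patient. The comparison of the two arms overall is not at stake.

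**Working it through.** The SAP gives no figure on this point, so there is none to reproduce. The questions are whether the open choice can alter a result, by how much, and whether closing it would help.

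**1. What is open.** Section 4e leaves open the model class (mixed model or regression), the factors and the form of the test. Both model classes can carry an arm-by-factor interaction, so neither choice rules out a proper test of effect modification.

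**2. Does model class alone matter?** There are two measurement times. Let D = week-14 value minus baseline value.

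- In a mixed model that leaves the baseline means free, the time × arm × factor term is the arm × factor difference in mean D. A regression of D on arm × factor estimates the same quantity. In six simulated complete datasets the two agreed in estimate and test statistic (for example 0.518 and 2.337 in both).
- A mixed model that constrains baseline gave the same estimate as a regression of the week-14 value on arm × factor plus baseline (ANCOVA), for example 0.369 in both.

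With complete data and the same treatment of baseline, choosing mixed model or regression therefore changes nothing. What can differ is how baseline enters.

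**3. How much could the treatment of baseline matter?** This was simulated with no true interaction.

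- From the SAP: 40 per arm (section 5: "we need 40 participants in each group"), and three factors, the number of examples in section 4e. Whether 40 follows from the stated effect size is a separate matter.
- Assumed: factors unrelated to outcome (two continuous, one binary), baseline to week-14 correlation of 0.3, 0.5 or 0.7, and an analyst who keeps the smaller p-value of the ANCOVA and change-score interaction models.
- 12,000 runs per setting; Monte Carlo standard error at most 0.004.

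| Correlation | One factor, smaller p | Rise | At least one of three, smaller p | Rise |
|---|---|---|---|---|
| 0.3 | 0.080 | 0.028 | 0.220 | 0.074 |
| 0.5 | 0.074 | 0.024 | 0.206 | 0.063 |
| 0.7 | 0.068 | 0.018 | 0.189 | 0.048 |

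A single fixed model gave 0.049-0.052 for one factor and 0.140-0.149 for at least one of three (theory: 0.05 and 1 − 0.95³ = 0.143). The rise is thus about 2-3 points for one factor and 5-7 for three under the assumed rule. By step 2 it is zero if baseline is treated alike.

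**4. Would tying section 4e to the primary model remove that rise?** No. Section 4c names mixed linear models but not whether baseline is constrained or left free. An interaction added to that model would inherit the same choice. The 14-15% for three factors would also remain if each interaction were tested at 0.05.

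**5. What can this analysis show at all?** Take two equal subgroups, so 20 patients per arm-by-subgroup cell, and an interaction of 0.5 SD, the size the SAP assumes for the main effect. The standard error is √(4/20) = 0.447 SD and 0.5/0.447 = 1.118. Power at two-sided 0.05 is Φ(1.118 − 1.960) = Φ(−0.842) ≈ 0.20. Whatever model is used, the result can only suggest a hypothesis.

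**The case for a change.** The strongest case for a change is that this is not mere silence. The SAP takes up the subject and expressly puts the decision after data completion, although sections 4c and 4d show that it could have been made already. A few sentences would settle it at no cost in patients or data, and calling an analysis exploratory does not tell the reader how its model was picked.

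Part of this stands. The postponement is real, nothing else in the SAP resolves it, and the text does not exclude a choice made with results by arm in view. Naming the interaction term would be tidier.

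Three things limit it:

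- A finished dataset is not the same as results already seen by arm. The wording fits equally well with a choice made on the extent and pattern of missing values, which section 4f says will be assessed.
- A reader of the SAP is told outright that the subgroup model was not fixed in advance and can discount the results accordingly.
- A sentence fixing the model class would leave open what matters more: the treatment of baseline in section 4c, the measure of severity (fibroscan, ultrasound and ALT/AST are all candidates), whether age is cut or continuous, and which outcomes are examined. It would record one choice without securing a different or safer conclusion.

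**Conclusion.** The description of section 4e is accurate, but it does not amount to a fault that needs correcting. Followed as written, the plan yields subgroup results that are openly not pre-specified, and leaves the primary comparison as it is. An analyst would naturally add an arm-by-factor term to the section 4c model and report the estimate as exploratory.

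The effect of the model-class choice itself is nil for complete data with baseline treated alike. The 2-3 and 5-7 point rises belong to an open baseline choice combined with an assumed habit of keeping the smaller p-value, and should not be charged to the postponement.

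The agreement between model classes was checked on complete data. With the 15% dropout allowed for in section 5 the two could differ somewhat; that difference was not quantified, and missing data are taken up in section 4f. The conclusion also rests on the subgroup results being presented as exploratory, as section 4e describes them.

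### Section 5 names strength training in only one of its two planning groups, but both trial arms receive it, so the 7-point planning difference is not shown to be the expected Arm A versus Arm B difference

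*SAP*

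**What the plan says.** Section 1 sets the comparison as "moderate continuous training combined with strength training versus high-intensity training combined with strength training". Section 2a repeats it arm by arm: "Arm A: Moderate continuous training combined with strength training" and "Arm B: High-intensity training combined with strength training". Strength training is common to both arms, and only the aerobic component changes.

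Section 5 is headed "A priori sample size: based on literature" and gives two planning lines. The first is "Group A: combined aerobic and strength training (primary outcome liver fat content): 30% (10,9" (percent), and the second is "Group B: interval training (primary outcome liver fat content): 37% (12,4" (percent). It then states "Effect size is 0.5" and "Given alfa of 0.05, with a power to achieve of 0.8 we need 40 participants in each group", and raises the number to 46 per group for 15% dropout. It names no source and does not explain why the difference between these two groups should carry over to Arms A and B.

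**The concern.** Section 5 uses the letters A and B in the same order as the trial arms, so its two lines read as the results expected in those arms. On their wording they describe something else. Group A has aerobic exercise plus strength work; Group B has interval training with no strength component named. Taken at face value, that contrast varies two things at once, the aerobic mode and the presence of strength training. The trial varies only the first.

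The justification of the sample size is what is at stake. A claim of 0.8 power is useful only if the planning difference is a reasonable expectation for the comparison being run. If part of the 7 points arose because one group did strength training and the other did not, that part need not appear when both arms do it. The randomised comparison itself and its analysis are unaffected.

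**Working it through.** **The two descriptions side by side**

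| | First group | Second group | What differs |
|---|---|---|---|
| Sections 1 and 2a | moderate continuous + strength | high intensity + strength | aerobic component |
| Section 5, as labelled | aerobic + strength | interval; strength not named | aerobic component and, on the wording, strength |

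The mismatch comes from the wording and does not depend on the arithmetic below.

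**Inputs.** From section 5: means 30 and 37; bracketed values 10.9 and 12.4; effect size 0.5; alpha 0.05; power 0.8; 40 per group; 15% dropout; 46 recruited. Assumptions not stated in the SAP: the bracketed values are SDs, and the test is an unadjusted two-sample t-test, two-sided unless noted.

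**The plan's own figure first**

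- Pooled SD = √((10.9² + 12.4²)/2) = √((118.81 + 153.76)/2) = 11.67.
- Implied standardised difference d = 7/11.67 = 0.60, against the stated 0.5.
- Normal approximation, two-sided: n per group = 2(1.96 + 0.842)²/d². This gives 63 at d = 0.5 and 44 at d = 0.60 (64 and 45 by t-test).
- One-sided, with 1.645 in place of 1.96: 50 at d = 0.5 and 35 at d = 0.60 (51 and 36 by t-test).

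None of these gives 40. A number near 40 appears only with assumptions that the SAP does not state. One example is baseline adjustment, which multiplies n by 1 − r²: 64 × (1 − 0.6²) = 40.96, so 41, at d = 0.5 with r = 0.6. With 40 per group, two-sided t-test power is 60% at d = 0.5 and 75% at d = 0.60.

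**Dropout.** 40 × 1.15 = 46 reproduces the stated recruitment. Losing 15% of 46 leaves 46 × 0.85 = 39.1, so about 39 evaluable per group.

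**Power if the true arm difference is not 7 points** (SD 11.67, two-sided t-test at 0.05, 40 per group; noncentrality = d√(40/2))

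| True difference (points) | d | Power |
|---|---|---|
| 3.5 | 0.30 | 26% |
| 5.25 | 0.45 | 51% |
| 7 | 0.60 | 75% |
| 8 | 0.69 | 86% |

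The rows at 3.5 and 5.25 are 50% and 75% of the planning difference. The row at 8 shows the opposite direction. All the differences other than 7 are illustrative; the SAP supplies none of them.

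**Detectable difference at 80% power** (same test)

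- 40 per group: d = 0.634, and 0.634 × 11.67 = 7.4 points.
- 39 per group: d = 0.643, and 0.643 × 11.67 = 7.5 points.

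**The case against.** The strongest reply is that the labels are shorthand. Group A's line also leaves out that the aerobic work is moderate and continuous, so the labels are visibly abbreviated, and interval training may stand for interval plus strength. The source is not named and cannot be checked here. Planning from the nearest available literature is ordinary practice, and nothing shows that a like-for-like estimate exists. This all stands as a limit on what can be concluded. It does not remove the point, because the line directly above names strength training and section 2a names it for both arms. If the label is shorthand, one clause saying so closes the gap.

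A reader might infer that the trial is therefore underpowered because part of the 7 points belongs to strength training. The document does not support that. Section 5 does not say whether 30% and 37% are remaining liver fat or a relative reduction. If they are reductions, the group without named strength work did better. Strength training that helps would then have narrowed the gap, and giving it to both arms could widen it.

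A reader might also infer that the 0.8 power is correct for a different comparison. That is not supported either: under the standard calculations above, 40 per group does not give 80% power at the stated 0.5, nor two-sided at the implied 0.60.

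Finally, the SAP makes no equivalence claim, so misreading a null result as equivalence is a risk for later reporting and not a fault in the text.

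**Conclusion.** The point holds in a limited form. As worded, section 5 does not show that its 7-point difference is the one to expect between Arms A and B, because strength training is named for one planning group and given to both trial arms. That Group B's source lacked strength training is not established, and neither the direction nor the size of any effect on power can be determined from the document. The range of 26% to 86% power over 3.5 to 8 points shows how much depends on the planning difference. It is not an estimate of the trial's power. It rests on reading the bracketed values as SDs and on an unadjusted two-sided t-test with 40 per group, whereas section 4c specifies mixed linear models. The power statement should be corrected; the design does not have to change.

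**What to change.** Keep 46 per group and amend section 5 in two places.

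1. Check the source of the Group B values. If it included strength training, say so. If it did not, stop presenting 30% versus 37% as the expected arm difference.
2. Restate the power claim as a detectable difference, for example:

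> With about 39 to 40 evaluable patients per group, an unadjusted two-sided t-test at alpha 0.05 has 80% power for a standardised difference of about 0.63 to 0.64 (about 7.4 to 7.5 points if the bracketed values are SDs). The planning values come from a comparison in which only one group is described as including strength training.

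Drop the last sentence if step 1 shows that both groups had strength training. A remark that a non-significant result will be reported with its confidence interval and not read as equivalence is optional.

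The cost is one paragraph and no additional patients. The downside is a less favourable power statement.

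### Section 5's sample-size figures do not agree: the quoted values imply an effect size of 0.60, not 0.5, and 40 per group does not give 80% power at either in an unadjusted two-sided test

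*SAP*

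**What the plan says.** Section 5 (A priori sample size) of the SAP takes two literature values for liver fat content: "Group A: combined aerobic and strength training (primary outcome liver fat content): 30% (10,9"%) and "Group B: interval training (primary outcome liver fat content): 37% (12,4"%). The next line reads "Effect size is 0.5". The conclusion follows: "Given alfa of 0.05, with a power to achieve of 0.8 we need 40 participants in each group". For attrition it adds: "Accounting for a 15% drop out rate we will recruit 46 patients in each group".

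Section 5 does not label the bracketed values and does not name a test, a sidedness or a baseline-to-follow-up correlation. Elsewhere, Section 3a provides for "baseline measurements of outcome variables", Section 3c for a second assessment at 14 weeks, and Section 4c for the analysis: "We will compare the outcomes between the two study arms using mixed linear models".

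**The concern.** The section gives every link of a standard calculation: two means, two apparent SDs, an effect size, alpha, power and a sample size. A reader should be able to go from each to the next, but two links break. The means and SDs do not give the effect size, and the effect size does not give the sample size.

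This is the only justification of trial size in the SAP. Both arms are active exercise programmes, so a null result is a realistic outcome. A reader who believes the trial had 80% power at 0.5 will take such a result as stronger evidence of similarity than it is.

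**Working it through.** **Inputs, all from SAP Section 5.** Means 30 and 37; bracketed values 10.9 and 12.4, read as SDs (an assumption); stated effect size 0.5; alpha 0.05; power 0.8; 40 per group needed; 46 per group recruited; dropout 15%. Equal group sizes. Because sidedness is not stated, both are shown. Power and sample size are from the noncentral t distribution for an unadjusted two-sample comparison.

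**Step 1: from means and SDs to effect size.**

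- Pooled SD = √((10.9² + 12.4²)/2) = √((118.81 + 153.76)/2) = √136.285 = 11.67.
- Effect size d = (37 − 30)/11.67 = 0.600. The plan says 0.5.
- With one arm's SD alone: 7/10.9 = 0.642; 7/12.4 = 0.565. Neither rounds to 0.5.
- SD that would give 0.5: 7/0.5 = 14.0, larger than either quoted value.

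**Step 2: trying to reproduce 40 per group.**

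| Effect size | Sides | n per group for 80% | Power at 40 per group |
|---|---|---|---|
| 0.5 (stated) | two | 64 | 59.8% |
| 0.5 (stated) | one | 51 | 71.6% |
| 0.600 (pooled SD) | two | 45 | 75.4% |
| 0.600 (pooled SD) | one | 36 | 84.5% |
| 0.642 (SD 10.9 only) | two | 40 | 81.0% |
| 0.565 (SD 12.4 only) | one | 40 | 80.5% |

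The plan's 40 does not come out at its stated effect size under either sidedness. It does come out in the last two rows, but these use effect sizes of 0.642 and 0.565, which contradict the stated 0.5.

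**Step 3: dropout.** 40 × 1.15 = 46, which is the plan's figure. But 46 × 0.85 = 39.1, so about 39 complete, one short of the 40 said to be needed. (40/0.85 = 47.1, so 48 would be required to keep 40.) With 39 per group, unadjusted two-sided power is 58.7% at 0.5 and about 74% at 0.600. The effect detectable with 80% power is 0.643 SD, or 0.643 × 11.67 = 7.5 percentage points. This step is minor; it costs about one percentage point of power.

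**Step 4: what baseline adjustment could add.** If the model uses the baseline value, and ρ is its correlation with the week-14 value, the effective effect size is d/√(1 − ρ²), with 2n − 3 degrees of freedom. For 80% two-sided power with 39 per group, ρ must be about 0.36 at d = 0.600 or about 0.63 at d = 0.5. Section 5 gives no value of ρ.

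**The case against.** The strongest reply is that the shortfall is computed for an analysis the SAP does not plan. Outcomes are measured at baseline and at 14 weeks and analysed with mixed models. If the model uses baseline, a correlation of 0.5 with 39 completers would give about 85% power at d = 0.60. The true power is therefore unknown rather than shown to be below 80%. That stands as a limit on the consequence: the powers above describe an unadjusted comparison only. It does not rescue the section, which invokes no correlation, and no correlation turns an effect size of 0.60 into 0.5. At d = 0.5 the same correlation of 0.5 would still leave power near 71%.

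Second, the brackets are unlabelled and the literature source is not shown, so 0.60 depends on reading them as SDs. That is the natural reading, but it remains an assumption. The conflict between 0.5, 40 and 0.8 does not depend on it.

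Third, the document does not show which figure is the slip. If 0.5 was the intended target, restating the effect as 0.60 would flatter the trial. This is a fair caution, and the fix allows for it.

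Fourth, a sample-size error biases neither the estimate nor the type I error rate. That is true, but the stated power is still wrong as written.

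**Conclusion.** The concern holds and must be fixed. The effect size of 0.5 does not follow from the quoted values, which give 0.60 if the brackets are SDs. Independently of that reading, 40 per group does not give 80% power at 0.5 in an unadjusted comparison under either sidedness.

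In an unadjusted two-sided test with 40 per group, a real difference would be missed about 40% of the time at 0.5 (1 − 0.598) or about 25% at 0.60 (1 − 0.754), against the 20% the plan implies. An unstated one-sided test at 0.60 would put 40 above the 36 needed, and an unstated baseline correlation could restore 80%, but the SAP documents neither. The finding is that the power claim is unsupported by its own inputs, not that the trial is proven underpowered.

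**What to change.** Keep 46 per group and rewrite Section 5 so that each figure follows from the one before:

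- Label the bracketed values as SDs and give the effect size as 7/11.67 = 0.60.
- State two-sided alpha 0.05 and the test assumed.
- Leave the recruitment inflation as it is and state about 39 evaluable per group after 15% dropout.
- State unadjusted power of about 74%, and a detectable effect at 80% power of about 0.64 SD (7.5 percentage points).
- If 0.5 was the intended target, say so, give its basis, and state 58.7% at 39 per group instead.
- If 80% is to be claimed, tie it to a baseline-adjusted analysis using the baseline values already collected, and state the assumed baseline-to-week-14 correlation. It must be about 0.36 or more at 0.60, or about 0.63 or more at 0.5. The value should come from data, not be chosen to reach 80%.

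This changes SAP wording only and needs no extra patients. The price is a less favourable unadjusted power figure. Holding 80% unadjusted at 0.60 would instead need 45 evaluable per group: 45/0.85 = 52.9, so 53 recruited per group, or (53 − 46) × 2 = 14 more patients in total.

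### Minor: at 15% dropout, recruiting 46 per group leaves about 39, just short of the 40 that section 5 of the SAP requires

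*SAP*

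**What the plan says.** Section 5 (A priori sample size) of the SAP gives the base requirement as "Given alfa of 0.05, with a power to achieve of 0.8 we need 40 participants in each group". The next sentence gives the recruitment target: "Accounting for a 15% drop out rate we will recruit 46 patients in each group". No inflation formula is shown, dropout is not defined, and nothing elsewhere in the SAP changes these figures.

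Two other sections bear on what a dropout costs. Section 3c plans one follow-up: "We will assess outcome measurements at the end of the 14-week intervention period". Section 4c defines the primary analysis as intention-to-treat by mixed linear models, "including all randomized participants, regardless of adherence or dropout".

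**The concern.** Three figures stand in two adjacent sentences: 40 needed, 15% lost, 46 recruited. If 15% of those recruited are lost, 46 does not leave 40. The recruitment target then fails to deliver, on the SAP's own dropout rate, the number that the SAP says it needs.

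Little is at stake for the trial as planned. The step matters more if it is reused: should the base sample size be recalculated, the same inflation would again give too few recruits, and the gap grows with the base size and the dropout rate.

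**Working it through.** **Inputs, all from section 5 of the SAP.** Needed per group: 40. Dropout: 15%. Recruited per group: 46. Alpha: 0.05, sidedness not stated. Target power: 0.8. Stated effect size: 0.5. Group figures: 30% (10.9%) and 37% (12.4%), with the bracketed values assumed to be standard deviations.

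**Reproducing the plan's figure.** 40 × (1 + 0.15) = 46.0, an exact match. The route is inferred, but the mismatch below does not depend on it.

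**Checking it against the stated dropout rate.**
- Expected to remain from 46: 46 × (1 − 0.15) = 39.1, which is 0.9 below 40.
- Recruits needed to keep 40: 40/(1 − 0.15) = 47.06. Recruiting 47 leaves 47 × 0.85 = 39.95, and rounding up to 48 leaves 48 × 0.85 = 40.8.
- Dropout that 46 can absorb: 1 − 40/46 = 6/46 = 13.0%.

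**Cost in power.** This uses a two-sample t-test at alpha 0.05, moving from 40 to 39 per group. Two effect sizes are used: the stated 0.5, and the value implied by the listed means and SDs, d = 7/√((10.9² + 12.4²)/2) = 7/11.674 = 0.60.

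| Test | d | Power, n = 40 | Power, n = 39 |
|---|---|---|---|
| Two-sided | 0.5 | 59.8% | 58.7% |
| Two-sided | 0.60 | 75.4% | 74.4% |
| One-sided | 0.5 | 71.6% | 70.7% |
| One-sided | 0.60 | 84.5% | 83.6% |

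The loss is about one percentage point in each row, and no row crosses 80% because of it.

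**Chance of keeping at least 40 in a group.** If each participant drops out independently with probability 15%, it is 45% with 46 recruited, 59% with 47 and 71% with 48. Dividing by 0.85 targets the expected number remaining and does not guarantee 40.

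**Would 48 repair the sample size?** No. With 40.8 remaining, two-sided power is about 61% at d = 0.5 and 76% at d = 0.60. For 80% power the t-test needs 63.8 per group (d = 0.5) or 44.6 (d = 0.60) two-sided, and 50.2 or 35.1 one-sided. None of these is 40.

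**If the base is recalculated.** With a base of 64, for example, 64 × 1.15 = 73.6, giving 74; 64/0.85 = 75.3, giving 76.

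**The case against.** The arithmetic is hard to dispute; the case on the other side concerns meaning and size.

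*The 15% may be an allowance added to 40.* On that reading the figures agree. But the text calls it a dropout rate, and such a rate is a share of those who enter. Adding it to the target is the slip itself.

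*The analysis keeps everyone.* Section 4c includes all randomised participants, and section 4f foresees multiple imputation where applicable. This stands in part: someone who stops training but attends the 14-week visit is not lost, so the shortfall concerns loss to assessment only. Someone lost before that single follow-up adds no post-baseline outcome. Neither the mixed model nor imputation restores much information about it.

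*The power figures come from an unadjusted t-test.* True. A mixed model that uses baseline values could gain more than one point, but the SAP does not specify the model closely enough to quantify this.

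*The shortfall is trivial, and 40 is itself unsound.* Both parts stand. The first is why the point is graded minor. The second means that the base size is the larger problem and that correcting the inflation alone would not secure 80% power. Neither makes the sentence in section 5 right.

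**Conclusion.** The point holds and is minor. At the stated dropout rate, 46 recruits per group leave about 39, not 40; 46 fits a dropout of 13%. The cost is about one participant per group and about one percentage point of power, and no planned analysis changes. The conclusion assumes that dropout is a proportion of those recruited and means loss to the 14-week assessment. The power figures further assume a two-sample t-test and that the bracketed values in section 5 are standard deviations. The requirement of 40 is taken as given here, although it does not follow from the SAP's own inputs.

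**What to change.** Reword the last sentence of section 5 in one of two ways: recruiting 46 per group leaves about 39 at 15% dropout; or recruiting 46 per group allows for 13% dropout while keeping 40. The second changes the planning assumption, and the SAP offers no support for 13%, so it should be used only if the sponsor considers that rate realistic. The cost is one sentence and no added participants.

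If the base size is recalculated, inflate the result by n/(1 − dropout) and show the formula. Moving from 46 to 47 or 48 should not be presented as a repair of the sample size while the base of 40 stands unexplained.
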